**Medications:**

Any medications that are considered necessary for the patient's welfare are given based on the decision of the treating physician.

---

**Informed consent:**

It is the responsibility of the investigator to obtain written informed consent from each patient participating in this study, after adequate explanation of the aims, methods and potential hazards of the study. An informed consent form will be signed. An additional signature

---

Protocol NI-0501-07 version 1.0, dated 12 Feb 2016

---

will be requested specifically for genetic analyses.

Patients may withdraw their consent at any time; it is the responsibility of the investigator to contact the sponsor for specific patient withdrawal of consent while maintaining the confidentiality by communicating only patient codes. The sponsor will proceed with the destruction of all left over patient material within 30 days. The sponsor will also inform and request confirmation from potential collaborators to destroy aliquots that may have been transferred under collaboration agreements for the purpose of the research described in this protocol. The data generated prior withdrawal of consent will be maintained.

---

**Data collection and patient confidentiality:**

Relevant clinical information including date of diagnosis, medical history and previous and current treatments will be gathered by the treating physician.

The investigator must assure that patients' anonymity will be maintained and that their identities are protected from unauthorized parties. On Data Collection Forms or other documents or material submitted to the sponsor, patients should not be identified by their names, but by an identification code. The investigator should keep a patient log showing codes, names and addresses. The investigator should maintain documents not for submission to NovImmune, e.g., patients' written consent forms, in strict confidence.

---

**Study administration:**

**Record Retention**

The investigator will ensure that essential records are kept in a secure archiving facility for the retention period stipulated in the study contract. Essential documents include, but are not limited to, the following:

- Signed informed consent documents for all patients
- Subject identification codes
- Record of all communications between the investigator and the IEC
- Composition of the IEC
- Record of communications between the investigator, NovImmune and their authorised representative

These records will be held in the Investigator's archives. If the Investigator is unable to meet this obligation, the Investigator must ask NovImmune for permission to make alternative arrangements.

---

---

Details of these arrangements should be documented in the clinical study centre TMF.

### **Financial Disclosure**

Investigator is required to provide financial disclosure information to allow NovImmune to submit complete and accurate certification or disclosure statements in accordance with applicable national and local regulations upon request. In addition, investigator must provide NovImmune with a commitment to promptly update this information if any relevant changes occur during the course of the investigation and for 1 year following the completion of the study.

### **Disclosure of Protocol and Study Results and Publication Policy**

Publication or communication of results will be decided upon completion of the study or earlier if data are considered sufficiently novel and robust. NovImmune will comply with the requirements for publication of results involving human research.

Authorship will be determined by mutual agreement and in line with ICMJE authorship requirements. Any formal publication of the study in which contribution of NovImmune personnel exceeded that of conventional monitoring will be considered as a joint publication by the investigator and the appropriate NovImmune personnel.

So-called ‘ghost writing’ is not permitted. All contributors who do not meet the criteria for authorship should be listed in an acknowledgments section. Examples of those who might be acknowledged include a person who provided purely technical help, writing assistance, or a department chairperson who provided only general support.

Any inventions and resulting patents, improvements, and/or know-how originating from the use of data from this study will become and remain the exclusive and unburdened property of NovImmune, except where agreed otherwise.

### **Monitoring and Auditing**

As the aim of this study is mainly to test blood for research purpose no specific monitoring at site is foreseen by NovImmune. However for compliance with applicable government regulations with respect to current GCP and standard operating procedures, direct access to the on-site study documentation and medical records must be ensured to any audit or inspections.

---

1 Abbreviations and definition of terms

AE	Adverse event
CSR	Clinical Study Report
FAS	Full Analysis Set
IFN γ	Interferon gamma
ICF	Informed consent form
LLOQ	Lower limit of quantification
HLH	Hemophagocytic lymphohistiocytosis
M-HLH	Malignancy-associated hemophagocytic lymphohistiocytosis
NI-0501	Emapalumab
pHLH	Primary hemophagocytic lymphohistiocytosis
SAE	Serious adverse event
SAP	Statistical Analysis Plan
Sobi	Swedish Orphan Biovitrum
ULOQ	Upper limit of quantification
PPS	Per Protocol Set

2 Introduction

This Statistical Analysis Plan (SAP) describes the planned analysis and reporting for Sobi protocol NI-0501-07 (An observational, multicenter study to evaluate interferon gamma (IFN γ) and other inflammatory mediators in patients with malignancy-associated hemophagocytic lymphohistiocytosis (M-HLH)).

This observational study is designed to provide a better understanding of the potential use of IFN γ and IFN γ -inducible chemokines as markers of M-HLH disease activity and potential prognosis and of the possible role of IFN γ as a therapeutic target in M-HLH, and to explore the genetic/ profiles in patients with M-HLH with regard to HLH-related genes in patients who are diagnosed with M-HLH.

The purpose of this SAP is to outline the exploratory analyses to be completed to support the synopsis for protocol NI-0501-07. The exploratory analyses identified in this SAP could be included in regulatory submissions and/or future manuscripts. Also, additional exploratory analyses not necessarily identified in this SAP may be performed to support the clinical

development program. Any post-hoc analyses not identified in this SAP will be clearly identified as such in the synopsis.

The structure and content of this SAP provides sufficient detail to meet the requirements identified by the FDA and International Conference on Harmonisation of Technical Requirements for Registration of Pharmaceuticals for Human Use (ICH): Guidance on Statistical Principles in Clinical Trials. All work planned and reported for this SAP will follow internationally accepted guidelines, published by the American Statistical Association and the Royal Statistical Society, for statistical practice.

3 Study objectives and endpoints

3.1 Study objectives

- To determine the levels of inflammatory markers including, but not limited to interferon gamma (IFN γ), interleukin 1 beta (IL1 β), interleukin 6 (IL-6), interleukin 10 (IL-10), interleukin 17 (IL-17), soluble IL-2 Receptor α (sCD25), C-X-C chemokine ligand 9 (CXCL9), C-X-C chemokine ligand 10 (CXCL10), C-XC chemokine ligand 11 (CXCL11), soluble CD163 (sCD163), neopterin and Tumor Necrosis Factor alpha (TNF α) in patients diagnosed with M-HLH and whenever possible, to monitor the evolution over time of these markers.
- To assess the relationship between the above-mentioned inflammatory cytokines and disease activity.
- To assess the relationship between genetic variants of the genes typically causing primary HLH and M-HLH and associated inflammatory markers.

3.2 Study endpoints

3.2.1 Inflammatory biomarkers

Level of

- CXCL10 (pg/mL)
- CXCL9 (pg/mL)
- IFNg V-PLEX (pg/mL)
- IL10 V-PLEX (pg/mL)
- IL1B V-PLEX (pg/mL)
- IL6 V-PLEX (pg/mL)
- Neopterin (nM)
- TNFa V-PLEX (pg/mL)
- Total hIFN γ (pg/mL)
- sCD163 (ng/mL)

- sIL2R α (pg/mL), also called sCD25

Note: No data reported for C-XC chemokine ligand 11 (CXCL11) and interleukin 17 (IL-17).

The biomarkers are measured in the M-HLH group and in the malignant control group without M-HLH.

3.2.2 Inflammatory biomarkers- correlation

The degree of correlations between inflammatory markers and between selected inflammatory markers and markers of disease activity (lab assessments) will be investigated.

The inflammatory biomarkers are as listed in section 3.2.1 and the other laboratory assessments as defined in the protocol are listed below

- Albumin
- AST, ALT, Alkaline Phosphatase
- Basophils
- β 2-microglobulin
- Total and conjugated Bilirubin
- BUN, serum creatinine
- CRP
- D-dimers
- Hemoglobin, Hematocrit, Red blood cells, white blood cells and differential count, platelets
- Fasting triglycerides
- Ferritin
- Fibrinogen
- Lactate dehydrogenase
- NK cell activity
- Serum IgG
- Sodium

3.2.3 Genetic variants

Genetic data was only available for 5 out of 19 patients in the HLH group and no analysis of genetic variants will be performed.

4 Study methods

4.1 Overall study design and plan

This is a non-interventional study designed to determine the levels of pro-inflammatory markers (as listed above) in patients diagnosed with M-HLH and to assess the relationship between the biomarkers and disease activity and prognosis during the M-HLH course. Inflammatory markers will also be measured in a group of control patients diagnosed with hematological malignancy in absence of HLH (as described above).

Data collection may be performed retrospectively if sufficient clinical information is available to allow for a meaningful interpretation of the biomarker results.

An approximate volume of 500 µl – 1 ml of serum or plasma is required per time point. Whenever possible, serum (and not plasma) should be collected, as this is the preferred matrix for the biomarker analysis.

In addition to the serum samples for the biomarker analysis, relevant information gathered by the treating physician will be collected in a data collection form. This will include information on the clinical presentation of M-HLH, the type of underlying malignancy, the date of onset of malignancy in relation to HLH manifestations, treatment regimen prior to and/or ongoing at the time of M-HLH onset, laboratory parameters, M-HLH disease activity (e.g. newly diagnosed, reactivation), specific HLH therapy with best response to the therapy, other concomitant medications, patient follow-up and disposition, stem cell transplant status, duration of response, and survival. Whenever possible, collection of serum samples for biomarker analysis and relevant information should occur at M-HLH diagnosis, at regular time intervals during the treatment course, at resolution and/or reactivation of the disease.

In addition to the above a minimum of 1 ml of whole blood will be collected (EDTA tubes) for genetic characterization and identification of the presence of genetic variants of the genes typically causing primary HLH. A specific consent for genetic testing must be given by the patient. Genetic samples may also be collected from existing bank of samples (frozen whole blood in EDTA or frozen extracted DNA), if proper consent has been obtained.

4.2 Selection of study population

Male and female (adult and children) patients who are diagnosed with M-HLH and that meet the inclusion criteria. In addition, patients with a diagnosis of hematological malignancy in the absence of HLH will be included as a control group.

4.3 Method of treatment assignment and randomization

This is an observational study (not randomized). Please see details on study population section 4.2

5 Sequence of planned analysis

5.1 Interim analyses

There was no planned interim analysis for this observational study.

5.2 Analyses and reporting

All final analyses identified in the protocol and in this SAP will be performed only after the database lock. A data review will be held prior to database lock. The SAP will be finalized, locked and signed prior to database lock.

Any post-hoc analyses included in the study synopsis which were not identified in this SAP, will be clearly identified as such in the relevant report section.

6 Sample size determination

No formal sample size was calculated for this observational study.

The protocol stated a minimum of 14 (maximum of 50) M-HLH patients will be studied, including a minimum of 7 non iatrogenic M-HLH and 7 iatrogenic M-HLH. A control group of 10 patients with a diagnosis of hematological malignancy in absence of HLH will also be evaluated.

A total of 39 patients were included in the study, 19 patients were diagnosed with M-HLH and 20 patients were included in the control group.

7 Analysis populations

The All enrolled set will be used in the statistical analyses as no study drug was administered.

7.1 All enrolled set

All subjects who signed an informed consent.

8 General issues for statistical analysis

No statistical tests will be presented. Only exploratory descriptive statistics will be displayed as described below:

Continuous data will be summarized using descriptive statistics: n, mean, standard deviation (SD), median, minimum, 1st quartile, 3rd quartile and maximum, unless otherwise indicated.

Minimum and maximum will be presented to the same number of decimal places as the raw data and mean, standard deviation and median will be presented to one more decimal place than the raw data.

Categorical data will be summarized using counts and percentages. Percentages will be suppressed when the count is zero, however the category will still be displayed. The denominator for all percentages will be the number of patients within the group for the population of interest, unless otherwise indicated. Percentages will be presented to one decimal place.

All data will be listed in individual patient data listings.

Statistical analyses will be performed using SAS software Version 9.4 or later (SAS Institute Inc, Cary, North Carolina, United States).

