**Statistical Analysis:**

All analyses are exploratory. Statistical analyses of the data collected in this study will be focused on providing tabular and graphical summaries of the levels of inflammatory markers and of the clinical features of the disease both at diagnosis and during the course of treatment. Levels of inflammatory markers will be compared between patients with active M-HLH and the control group (i.e. hematological malignancy in absence of HLH). In addition, the degree of correlation between inflammatory markers, and between inflammatory markers and the severity of clinical manifestations, response to therapy, and survival of the patients will be assessed. Analyses may also be performed to study these relationships in various subgroups of patients, depending on the demographic, genetic and clinical characteristics observed, including *a posteriori* diagnosis based on HLH-2004 diagnostic criteria (Henter et al., 2007).

Criteria for diagnosis are:

- i) Fever
- ii) Splenomegaly
- iii) Cytopenia (affecting  $\geq 2$  of 3 lineages in peripheral blood):
  - Hb  $<90$  g/L (in infants  $< 4$  weeks: Hb  $<100$  g/L)
  - Platelets  $<100 \times 10^9$ /L
  - Neutrophils  $<1.0 \times 10^9$ /L
- iv) Hypertriglyceridemia and/or hypofibrinogenemia: Fasting triglycerides  $\geq 3.0$  mmol/L; Fibrinogen  $\leq 1.5$  g/L
- v) Hemophagocytosis in bone marrow or other specimens
- vi) Low or absence NK-cell activity (according to local laboratory reference)
- vii) Ferritin  $\geq 500$   $\mu$ g/L
- viii) sCD25  $\geq 2400$ U/ml

---

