8.3 Multiple comparisons and multiplicity

No comparison and multiplicity adjustment will be performed, only descriptive statistics.

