12.1 Inflammatory biomarkers

The inflammatory biomarkers as listed in section 3.2.1 will be displayed in scatter plots grouped by HLH and non-HLH group as in the below example.

For the HLH group the biomarker value closest to the date of HLH diagnosis (value must be after HLH diagnosis) will be used if more than one sample is available. For the non-HLH group the minimum and maximum value will be used and displayed in different colours/markers. If just one value available that value will be displayed with the same colour/marker as the HLH group. Biomarker data will be summarized by group using descriptive statistics and presented for HLH patients, non-HLH patients and overall.

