13.3 Vital signs

Weight and Height are only collected at screening/ICF. They will be presented as part of the Demographic table (see Section 10.1).

14 Changes from the planned analyses in the clinical trial protocol

No data reported for C-XC chemokine ligand 11 (CXCL11) and interleukin 17 (IL-17), hence no analyses performed for these biomarkers.

Genetic information was only obtained from 5 out of 19 HLH patients, no analysis on genetic variants will be performed.

15 References

N/A

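### The protocol promises a comparison of marker levels between active M-HLH and controls, but the SAP plans no between-group estimate or interval and does not list this as a change

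*SAP*

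**What the plan says.** The protocol's Statistical Analysis section opens with "All analyses are exploratory" and puts the emphasis on tables and graphs. A separate sentence then adds: "Levels of inflammatory markers will be compared between patients with active M-HLH and the control group". It names no test, effect measure or interval.

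SAP Section 8 says "No statistical tests will be presented. Only exploratory descriptive statistics will be displayed as described below". The list that follows is within-group: "Continuous data will be summarized using descriptive statistics: n, mean, standard deviation (SD), median, minimum, 1st quartile, 3rd quartile and maximum". Section 8.3 says "No comparison and multiplicity adjustment will be performed, only descriptive statistics". Section 12.1 gives scatter plots by group and adds "Biomarker data will be summarized by group using descriptive statistics and presented for HLH patients, non-HLH patients and overall". Section 12.4 presents the two groups separately.

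For M-HLH patients with several samples, Section 12.1 takes the one nearest to, and after, the HLH diagnosis. For controls, "For the non-HLH group the minimum and maximum value will be used and displayed in different colours/markers". It does not say which control value enters the summary table.

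Section 14, on changes from the protocol's planned analyses, has two entries. One is "No data reported for C-XC chemokine ligand 11 (CXCL11) and interleukin 17 (IL-17), hence no analyses performed for these biomarkers". The other is the omission of the genetic analysis. The between-group comparison is not mentioned.

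**The concern.** Leaving out p-values is a reasonable choice in a small exploratory study. Leaving out any estimate of the difference, with its uncertainty, is a separate choice, and the SAP gives no reason for it. The protocol named a comparison between the two groups, and the SAP contains no quantity that expresses it.

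SAP Section 2 says the study should inform the use of IFNγ and its chemokines as disease markers and IFNγ as a possible target, and that the analyses may go into regulatory submissions or manuscripts. A reader of those outputs would see two columns of summaries and a plot, and would have to judge by eye how far apart the groups are and how firmly that is known. If an estimate were added later, Section 5.2 would require it to be labelled post hoc, although the protocol had foreseen a comparison.

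**Working it through.** **Is there a figure to reproduce?** No. SAP Section 6 says no formal sample size was calculated, and neither document gives an effect size, SD or precision target for this contrast. The only arithmetic is the enrolment total: 19 + 20 = 39, which agrees with Section 6.

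**Is a contrast defined anywhere?** Taking the places in turn:
- Protocol, Statistical Analysis: a comparison with controls is promised, with no measure named.
- SAP 8: no tests; within-group statistics only.
- SAP 8.3: description only.
- SAP 12.1 and 12.4: summaries and plots by group.
- SAP 14: silent on the point.

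So no between-group estimate or interval is specified.

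**How much uncertainty goes unstated?** Inputs: n₁ = 19 and n₂ = 20 (SAP Section 6), and one value per patient. The last is an assumption, since Section 12.1 uses two values for controls with several samples. The 19 is an upper limit, because Section 12.1 requires a sample after diagnosis.

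1. 95% half-width for a difference in means, in SD units: t(0.975, 37) × √(1/19 + 1/20) = 2.026 × 0.3204 = 0.649. At the protocol's minimum of 14 M-HLH patients and 10 controls, the same formula gives 0.859, so the actual enrolment is the better position.
2. On a ratio scale an SD must be assumed, as the documents give none. For a natural-log SD of 1.0, exp(0.649 × 1.0) = 1.91. For 1.5, exp(0.649 × 1.5) = 2.65. Over that range, a ratio of geometric means is known only to within a factor of 1.9 to 2.65 either way.
3. For an AUC (the probability that an M-HLH value exceeds a control value), the Hanley-McNeil variance is [A(1−A) + (n₁−1)(Q₁−A²) + (n₂−1)(Q₂−A²)] / (n₁n₂), with Q₁ = A/(2−A) and Q₂ = 2A²/(1+A). At A = 0.80, Q₁ = 0.667 and Q₂ = 0.711, so the variance is (0.16 + 0.48 + 1.351)/380 = 0.00524. The SE is 0.0724 and the half-width is 1.96 × 0.0724 = 0.142. The same formula gives 0.184 at A = 0.5 and 0.103 at A = 0.9.

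**Can a reader rebuild the contrast from the summaries?** Only crudely. Section 12.2 allows that markers may be log-normal, but Section 8 lists no geometric mean or log-scale SD. The control value is also ambiguous. For independent normal samples within a patient (assumption), the expected gap between maximum and minimum is 1.13, 1.69 or 2.33 within-patient SDs for 2, 3 or 5 samples (simulation). The implied contrast therefore depends on which control value is summarised.

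**The case against.** The strongest reply is that nothing has been dropped. The protocol calls every analysis exploratory, focuses on tables and graphs, and never named a ratio, shift, AUC or interval. In that setting, group summaries side by side are a fair reading of a comparison. Section 8.3 sits under a multiplicity heading and is loosely worded; it may mean only that no multiplicity adjustment is made. Group n, mean, SD, quartiles, range, scatter plots and individual listings are all planned, so overlap between the groups will be visible. The groups are non-randomised, samples may be retrospective and no matching is described, so formal intervals could suggest more weight than the design carries.

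Much of this stands. A reader might infer that the SAP forbids any comparison, or that it has removed the study's central analysis. The documents do not support either reading. Section 8.3 is ambiguous, an informal comparison remains possible, and none of the three objectives in the protocol or SAP Section 3.1 names the contrast with controls.

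What the reply does not remove is that, on any reading of Section 8.3, no section defines a contrast, and Section 14 does not say that the comparison will be descriptive only. Exploratory status does not argue against an interval: the protocol used that label and still promised the comparison. Confounding calls for careful labelling, but does not justify leaving sampling uncertainty unstated.

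**Conclusion.** The point holds as a gap in estimation and disclosure. The comparison promised in the protocol has no between-group estimate or interval in the SAP, and Section 14 does not declare this. It is not a wrong figure, and the absence of tests is not a fault.

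The unstated uncertainty is material: about 0.65 SD either way for a mean difference, or about 0.14 either way for an AUC of 0.80. These assume one value per patient and all 19 and 20 patients contributing; fewer usable M-HLH samples would widen them. The ratio factors of 1.9 to 2.65 rest wholly on the assumed log SD. Group size does not explain the omission, since enrolment exceeds the protocol's 14 M-HLH minimum and its 10 controls.

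**What to change.** In SAP Section 12.1, for each of the 11 measurements listed in Section 3.2.1 (IFNγ appears under two assays):

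- **Use one pre-defined value per patient.** For M-HLH, keep the existing rule of the value closest to and after diagnosis. For controls, replace the minimum-and-maximum pair with a single value chosen without regard to its level, for example the first available sample. Without this step no contrast is well defined.
- **Report one rank-based contrast with a 95% confidence interval:** the AUC, or a Hodges-Lehmann shift on the log scale. Either is less sensitive than a ratio of geometric means to the LLOQ/2 and ULOQ substitutions in Section 8.4.2. Choose an interval method that respects the upper limit of 1: at an AUC of 0.9 the symmetric interval reaches 0.9 + 0.103 = 1.003.
- **Label the results** exploratory, unadjusted and from unmatched groups, with no p-values. Reword Sections 8 and 8.3 to permit this.

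If the sponsor keeps descriptive summaries only, add a sentence to Section 14 saying that the protocol's comparison will be descriptive, with the reason.

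The cost is SAP wording, a decision on the control value, and an estimate and interval per marker in one table; no new data. The intervals will be wide, some separations will look less decisive, and none should be read as confirmatory. If the SAP has already been finalised, Section 5.2 would require the estimates to be marked post hoc.
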